### 9.3.2 Exclusion Criteria

1. Females of childbearing potential

NOTE: All females will be considered to be of childbearing potential unless they are postmenopausal (amenorrheic for at least 12 consecutive months, in the appropriate age group, and without other known or suspected cause) or have been sterilized surgically (ie,

bilateral tubal ligation, total hysterectomy, or bilateral oophorectomy, all with surgery at least 1 month before dosing).

2. A current diagnosis of restless legs syndrome, periodic limb movement disorder, circadian rhythm sleep disorder, or narcolepsy
3. Reports symptoms potentially related to narcolepsy, that in the clinical opinion of the investigator indicate the need for referral for a diagnostic evaluation for the presence of narcolepsy
4. A history of symptoms of REM Behavior Disorder, sleep-related violent behavior, sleep-driving, or sleep-eating, or symptoms of another parasomnia that in the investigator's opinion make the subject unsuitable for the study
5. Periodic Limb Movement with Arousal Index (PLMAI) as measured on the screening PSG:
  - Age 18 to <65 years: PLMAI  $\geq 10$
  - Age  $>65$  years: PLMAI  $>15$
6. A prolonged QTcF interval (QTcF  $>450$  ms) as demonstrated by a repeated ECG at Screening
7. Any suicidal ideation with intent with or without a plan at Screening or within 6 months of Screening (ie, answering "Yes" to questions 4 or 5 on the Suicidal Ideation section of the C-SSRS)
8. Any lifetime suicidal behavior (per the Suicidal Behavior section of the C-SSRS) within 10 years of Screening
9. Evidence of clinically significant disease (eg, cardiac, respiratory, gastrointestinal, renal disease) that in the opinion of the investigator(s) could affect the subject's safety or interfere with the study assessments
10. Hypersensitivity to the study drug or any of the excipients
11. Used any prohibited prescription or over-the-counter medications within 1 week or 5 half-lives, whichever is longer, before the screening PSG
12. Any history of or concomitant medical condition that in the opinion of the investigator(s) would compromise the subject's ability to safely complete the study
13. Scheduled for surgery during the study that requires general anesthesia or administration of prohibited medications
14. Psychotic disorder(s) or unstable recurrent affective disorder(s) evident by use of antipsychotics or prior suicide attempt(s) within approximately the last 2 years
15. History of drug or alcohol dependency or abuse within approximately the last 2 years
16. Use of illegal recreational drugs (includes marijuana, regardless of whether prescribed for medicinal use)
17. Currently enrolled in another clinical study or used any investigational drug or device within 28 days or 5 $\times$  the half-life, whichever is longer preceding informed consent
18. Previously participated in other clinical trial of lemborexant
19. Exposure within the last 14 days to an individual with confirmed or probable corona virus disease 2019 (COVID-19) or symptoms within the last 14 days that are on the most

recent Centers for Disease Control and Prevention (CDC) list of COVID symptoms or any other reason to consider the subject at potential risk for an acute COVID-19 infection (revised per Amendment 01)

Additional Exclusion Criteria (OSA Cohort)

20. SpO2 <80% for  $\geq 5\%$  of TST during the screening PSG
21. Use of a CPAP device or dental appliance within 2 weeks of the screening PSG, and does not agree to abstain from the use of a CPAP device or dental appliance from the Screening Visit through the last study visit
22. Current evidence of a clinically significant, active respiratory disorder other than OSA. This includes bronchiectasis, emphysema, asthma, COPD or any other pulmonary disorder identified by review of medical history, physical examination, and which in the opinion of the investigator, could compromise the subject's safety or interfere with study assessments.
23. Current evidence of other clinically significant disease (eg, psychiatric disorders, disorders of the gastrointestinal tract, liver, kidney, respiratory system, endocrine system, hematological system, neurological system, cardiovascular system, or a congenital abnormality), malignancy within the past 5 years (other than adequately treated basal cell carcinoma or in situ carcinoma of the cervix), or chronic pain that in the opinion of the investigator could affect the subject's safety or interfere with the study assessments. Subjects for whom a sedating drug would be contraindicated for safety reasons because of the subject's occupation or activities are also excluded. Subjects with insomnia disorder, who complain of difficulties with sleep onset and/or sleep maintenance, are eligible provided that they meet this criterion. Note that medications to treat insomnia are prohibited.

Additional Exclusion Criteria (COPD Cohort)

24. Use of continuous ( $>16$  h/day) oxygen therapy
25. Use of oxygen therapy during PSG
26. Determination that, in the opinion of the investigator, removal of oxygen therapy could affect the subject's safety or interfere with the study assessments
27. Recent changes to COPD medications or recent acute exacerbation of COPD (ie, needing hospitalization or treatment with oral corticosteroids and/or antibiotics) within 3 months of enrollment (revised per Amendment 01)
28. On screening spirometry:
  - FEV1/FVC  $\geq 0.70$
  - FEV1  $\geq 80\%$  predicted (GOLD 1 Classification for mild COPD)
  - FEV1  $<30\%$  predicted (GOLD 4 Classification for very severe COPD)
29. On screening PSG:
  - Moderate to severe OSA (AHI  $\geq 15$ )
  - SpO2 <90% during wakefulness (supine and sitting)
  - SpO2 during sleep <80% for 25% or more of the recording with  $>5$  consecutive minutes <80% and any SpO2 reading <70%
30. ECG evidence of right ventricular hypertrophy or right heart failure

31. Screening hematocrit >55%
32. Use of a CPAP device or dental appliance within 2 weeks of the screening PSG, and does not agree to abstain from the use of a CPAP device or dental appliance from the Screening Visit through the last study visit
33. Current evidence of a clinically significant, active respiratory disorder other than COPD and mild OSA. This includes any other pulmonary disorder identified by review of medical history, physical examination, and which in the opinion of the investigator, could compromise the subject's safety or interfere with study assessments.
34. Current evidence of other clinically significant disease other than COPD and mild OSA (eg, psychiatric disorders, disorders of the gastrointestinal tract, liver, kidney, respiratory system, endocrine system, hematological system, neurological system, cardiovascular system, or a congenital abnormality), malignancy within the past 5 years (other than adequately treated basal cell carcinoma or in situ carcinoma of the cervix), or chronic pain that in the opinion of the investigator could affect the subject's safety or interfere with the study assessments. Subjects for whom a sedating drug would be contraindicated for safety reasons because of the subject's occupation or activities are also excluded. Subjects with insomnia disorder, who complain of difficulties with sleep onset and/or sleep maintenance, are eligible provided that they meet this criterion. Note that medications to treat insomnia are prohibited.

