15. History of drug or alcohol dependency or abuse within approximately the last 2 years
16. Use of illegal recreational drugs (includes marijuana, regardless of whether prescribed for medicinal use)
17. Currently enrolled in another clinical study or used any investigational drug or device within 28 days or 5× the half-life, whichever is longer preceding informed consent
18. Previously participated in other clinical trial of lemborexant
19. Exposure within the last 14 days to an individual with confirmed or probable corona virus disease 2019 (COVID-19) or symptoms within the last 14 days that are on the most recent Centers for Disease Control and Prevention (CDC) list of COVID symptoms or any other reason to consider the subject at potential risk for an acute COVID-19 infection (revised per Amendment 01)

Additional Exclusion Criteria (OSA Cohort)

20. SpO2 <80% for ≥5% of TST during the screening PSG
21. Use of a continuous positive airway pressure (CPAP) device or dental appliance within 2 weeks of the screening PSG, and does not agree to abstain from the use of a CPAP device or dental appliance from the Screening Visit through the last study visit
22. Current evidence of a clinically significant, active respiratory disorder other than OSA. This includes bronchiectasis, emphysema, asthma, COPD, or any other pulmonary disorder identified by review of medical history, physical examination, and which in the opinion of the investigator, could compromise the subject's safety or interfere with study assessments.
23. Current evidence of other clinically significant disease (eg, psychiatric disorders, disorders of the gastrointestinal tract, liver, kidney, respiratory system, endocrine system, hematological system, neurological system, cardiovascular system, or a congenital abnormality), malignancy within the past 5 years (other than adequately treated basal cell carcinoma or in situ carcinoma of the cervix), or chronic pain that in the opinion of the investigator could affect the subject's safety or interfere with the study assessments. Subjects for whom a sedating drug would be contraindicated for safety reasons because of the subject's occupation or activities are also excluded. Subjects with insomnia disorder, who complain of difficulties with sleep onset and/or sleep maintenance, are eligible provided that they meet this criterion. Note that medications to treat insomnia are prohibited.

Additional Exclusion Criteria (COPD Cohort)

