## **Inclusion and Exclusion Criteria for the OSA and COPD Cohorts**

The eligibility criteria in Study 113 are largely standard for safety studies in subjects, with particular criteria that are standard for studies of sleep agents (exclusion of significant periodic limb movement disorder or parasomnias; certain restrictions on habitual bedtime). Insomnia disorder is not specifically excluded unless subjects habitually sleep less than 5.5 hours. The screening PSG will be key for inclusion, since subjects tend to sleep less well in a sleep laboratory than at home. This is important since the AHI tends to be higher during REM sleep, which is more frequent during the second half of the night, the time when elderly poor sleepers tend to be awake.

Of note, CPAP and oral devices will be prohibited throughout the study. The study requires uncorrected values for AHI. The phenomenon of “CPAP washout” has been reported, in which, following cessation of CPAP use, AHI increases gradually over days or weeks ([Vroegop, et al., 2015](#)). Although the existence of this phenomenon is not universally accepted, there is no doubt that daytime sleepiness increases when CPAP is stopped, and those patients with OSA will accommodate to the increased levels of sleepiness, but that takes time, and the duration varies among patients. To avoid dosing with LEM (which may cause somnolence during the day in some subjects) against an unstable baseline of daytime sleepiness, Study 113 requires that CPAP not be used from 2 weeks before the screening PSG until the end of the second treatment period. This should not interfere with the medical care of OSA patients, or be a significant impediment to recruitment; many patients do not tolerate CPAP, such that non-compliance rates are high, as stated above. Further, the exclusion criterion specifies that there must not be a requirement that subjects use CPAP during the study, thereby excluding any for whom CPAP is a medical necessity. Whether subjects had been prescribed CPAP or other treatments for OSA in the past will be noted at Screening.

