#### **9.4.7 Prior and Concomitant Therapy**

Any medication (including OTC medications) or therapy administered to the subject during the study (starting at the date of informed consent or 90 days before first dose/administration of study drug, if appropriate) will be recorded on the Prior & Concomitant Medication case report form (CRF) or Non-Pharmacological Procedures CRF. The investigator will record on the AE CRF any AE for which the concomitant medication/therapy was administered.

Subjects with OSA will be required to abstain from using a CPAP device or dental appliance for at least 2 weeks before the screening PSG, and throughout the study (until after the EOS Visit).

Subjects must abstain from the use of recreational drugs throughout the study. No alcohol will be permitted in the clinic.

Prohibited medications should not be used during the study. A subject must not have used any prohibited prescription or over-the-counter medications within 1 week or 5 half-lives, whichever is longer, before Screening Visit 2. Prohibited medications include strong and moderate cytochrome P450 (CYP)3A inhibitors and strong and moderate CYP3A inducers. Prohibited medications also include any pharmacological treatment for insomnia disorder, including any medications (hypnotics or medications with known sedating effects) that are used for the purpose of inducing sleep or for treating OSA. These prohibitions apply even if the entire class to which that medication belongs is not prohibited (eg, anticonvulsants).

If a medication is not specified as prohibited but is in the same class as a medication and if the investigator is uncertain whether the medication has known sedating or alerting effects, the Medical Monitor must be consulted.

If a subject starts any prohibited medication or therapy, he/she must discontinue from the study, with the exception that certain prohibited medications may be used for a short duration (not to exceed 2 weeks) to treat an acute condition if this is agreed with the Medical Monitor. Note that strong and moderate CYP3A inhibitors and strong and moderate CYP3A inducers will not be permitted at any time for any duration during the study.

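### The CPAP exclusions apply only when recent use and refusal to abstain occur together, which contradicts the protocol's unconditional 2-week abstention rule

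*Protocol*

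**What the plan says.** Protocol section 9.3.2 has one CPAP criterion per cohort: exclusion 21 for OSA and exclusion 32 for COPD. Both read "Use of a CPAP device or dental appliance within 2 weeks of the screening PSG, and does not agree to abstain", and the agreed abstention runs "from the Screening Visit through the last study visit". The synopsis copies use the same connector ("device or dental appliance within 2 weeks of the screening PSG, and does not agree to abstain"). No other numbered eligibility criterion mentions CPAP or dental appliances.

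The abstention rule is also stated in two other ways:

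- Section 9.4.7, with the same text in the synopsis: "Subjects with OSA will be required to abstain from using a CPAP device or dental appliance for at least 2 weeks before the screening PSG". This rule then runs until after the EOS Visit. It does not depend on what the subject agrees to.
- Section 9.2, under a heading naming both the OSA and COPD Cohorts: the study "requires that CPAP not be used from 2 weeks before the screening PSG until the end of the second treatment period".

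Section 9.2 gives the reasons. One is "The study requires uncorrected values for AHI". It also mentions a reported washout effect, in which after CPAP is stopped "AHI increases gradually over days or weeks", and it wants to avoid dosing while daytime sleepiness is still unstable.

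**The concern.** An exclusion criterion built from two conditions joined by a conjunction applies only to subjects who meet both. Section 9.3 makes the numbered criteria the test for receiving study drug. A site that applies exclusion 21 or 32 as printed can therefore admit a subject whom sections 9.2 and 9.4.7 say should not be in the study.

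The screening PSG is most at stake. Its AHI decides OSA entry (15 or more) and COPD entry (below 15). The SAP's moderate and severe OSA subgroups (section 5.3.4) use the same AHI cut-points. If AHI is still recovering from recent CPAP use, the screening value understates the untreated one. The first treatment night, which supplies the Day 1 secondary endpoints for Period 1, comes soon afterwards and is exposed in the same way.

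**Working it through.** **Step 1: the logic of exclusions 21 and 32.** There are two yes/no facts: use within 2 weeks of the screening PSG, and refusal to abstain.

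| Recent use | Refuses to abstain | Excluded as written | Compatible with section 9.4.7 (subjects with OSA) |
|---|---|---|---|
| No | No | No | Yes |
| No | Yes | No | No |
| Yes | No | No | No |
| Yes | Yes | Yes | No |

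Three of the four combinations conflict with the abstention rule. The criterion catches one of them.

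**Step 2: how short the interval can be.** The inputs are the visit windows in Protocol Table 4 (Visit 1 on Day -21 to -8, Visit 2A on Day -15 to -2, no Day 0, dosing nights on Days 1, 8, 23 and 30) and section 9.1.1.1, which puts the screening PSG at least 6 days after the first screening visit. Suppose a recent user stops at Visit 1.

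- Days off CPAP at the screening PSG: minimum 6 (for example Day -8 to Day -2) and maximum 21 - 2 = 19.
- Largest shortfall against 2 weeks: 14 - 6 = 8 days. Any gap of 6 to 13 days falls short; a gap of 14 to 19 days does not.
- Minimum at Period 1 Day 1: 1 - (-8) - 1 = 8 days.
- Minimum at Period 1 Day 8: 8 - (-8) - 1 = 15 days.
- Minimum at Period 2 Day 8 (Day 30): 30 - (-8) - 1 = 37 days.

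The criterion does not say which screening visit starts the abstention. Sections 9.5.1.1.1 and 9.5.1.1.2 use the term for the visit at which demography and history are taken, which Table 4 places at Visit 1, so Visit 1 is the natural reading. If Visit 2 were meant, the agreement would begin only at the PSG visit itself, and the minimum would be 1 - (-2) - 1 = 2 days at Period 1 Day 1 and 8 - (-2) - 1 = 9 days at Period 1 Day 8.

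**Step 3: when abstention ends, and what is attributed to the criterion.** The criteria say the last study visit, section 9.4.7 says after the EOS Visit, and section 9.2 says the end of the second treatment period. Section 9.2 also says the exclusion criterion rules out subjects with a requirement to use CPAP. Neither exclusion 21 nor exclusion 32 contains this.

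**Step 4: the plan's power figure.** The stated OSA power is 82%. With combined within-subject variance 26.96, 30 completers, margin 5, true difference 1.5 and one-sided 0.05, the standard error is sqrt(2 x 26.96 / 30) = 1.341 and the noncentrality is (5 - 1.5) / 1.341 = 2.61. Noncentral t with 28 degrees of freedom gives 81.6%, so the figure reproduces. It has no term for CPAP washout, and a wording correction leaves it unchanged.

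**The case against.** The strongest reply is that the rule exists and the criterion is only loosely worded. Section 9.4.7 binds subjects with OSA without condition, so enrolling a recent user would be a protocol breach even if exclusion 21 did not stop it. Section 9.1.2 also has subjects instructed on the CPAP and dental-appliance prohibition during treatment. This stands as far as it goes: conduct is covered. It does not mend the eligibility test, because 9.4.7 sits under concomitant therapy and a site screening against 9.3 would reach a different answer.

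Second, section 9.2 says itself that the washout effect is not universally accepted, and it ties the 2-week interval most directly to daytime sleepiness. That is fair. The need for uncorrected AHI is nonetheless stated in the same paragraph.

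Third, a residual CPAP effect lowers AHI, so at the OSA threshold of 15 it would tend to reject eligible subjects, not admit ineligible ones. This is correct. In the COPD Cohort the direction reverses: a temporarily low AHI could pass the below-15 limit. A severe OSA subject could also be classed as moderate, although that subgroup analysis is run only if numbers suffice.

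A reader might infer that the COPD Cohort has no 2-week rule apart from exclusion 32, because 9.4.7 speaks of subjects with OSA. The documents do not support this. Section 9.2 is headed for both cohorts, and COPD subjects with the permitted mild OSA could also be read as subjects with OSA. The reach of 9.4.7 into that cohort is unclear, not absent.

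**Conclusion.** The inconsistency is real and is one of logic and wording. As written, exclusions 21 and 32 pass two kinds of subject whom the abstention rule would bar, and one kind may reach the screening PSG with about 6 days off CPAP where 14 are required elsewhere. The 6-day figure assumes that the subject stops at Visit 1 and the shortest permitted interval follows. The exposure falls on the screening AHI and the Period 1 Day 1 endpoints. Exposure of the severity split assumes it is made on the screening AHI; SAP section 5.3.4 does not name the night.

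Two stronger inferences should not be drawn:

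- **Loss of power or bias in the OSA primary analysis.** A power loss would need the share of recent users and the change in their AHI between the two Day 8 nights. The documents give neither. A complying subject who stopped at Visit 1 is already at least 15 days off CPAP at the first of those nights, so the effect there is likely small. Sequences are randomized 1:1 and the model has a period effect, so average drift would go into that effect and uneven drift into noise. No treatment bias is claimed.
- **A compromised SpO2 baseline.** Section 9.2 names AHI and daytime sleepiness. It does not give protection of SpO2 as a purpose of the rule.

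**What to change.** Reconcile exclusions 21 and 32 and their synopsis copies with section 9.4.7, its synopsis counterpart and section 9.2. After reconciliation, these passages should agree on:

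- how the two conditions in the criterion combine;
- which cohorts, and which subjects in the COPD Cohort, the 2-week rule covers;
- whether it covers dental appliances as well as CPAP, since the 2-week sentence in section 9.2 names only CPAP;
- which visit starts the agreed abstention, and when abstention ends;
- whether the criterion contains the statement about required CPAP use that section 9.2 attributes to it.

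Which rule should prevail is for the sponsor's clinical team; this review does not choose one. The cost is a protocol clarification of two criteria and their cross-references. Depending on how the passages are reconciled, a few subjects might be screened later. The sample size and analysis model do not change.

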## 9.4 Treatments

### 9.4.1 Treatments Administered

The following treatments will be administered to subjects in this study:

- lemborexant 10-mg film-coated tablets, taken immediately (within 5 minutes) before "lights off"
- lemborexant-matched placebo tablets, taken immediately (within 5 minutes) before "lights off"

**Table 1      Treatments Administered (OSA Cohort)**

Treatment Sequence	Treatment Periods in the OSA Cohort	
	1 (8 nights)	2 (8 nights)
A	lemborexant-matched placebo	lemborexant 10 mg
B	lemborexant 10 mg	lemborexant-matched placebo

**Table 2      Treatments Administered (COPD Cohort)**

Treatment Sequence	Treatment Periods in the COPD Cohort	
	1 (8 nights)	2 (8 nights)
C	lemborexant-matched placebo	lemborexant 10 mg
D	lemborexant 10 mg	lemborexant-matched placebo

#### 9.4.2 Identity of Investigational Product(s)

Lemborexant will be supplied by the sponsor in labeled containers.

Study drug must be stored as instructed on the study drug label. Study drug must be kept in a secure location and carefully stored at the study site within its original container. The sponsor will provide the study drug packaged as double-blinded supplies. Each subject's study drug will consist of lemborexant tablets supplied in bottles.

